### **8.5 Blood Volume**

Total blood sampling volume for an individual subject is shown in [Table 9.c.](#)

**Table 9.c Approximate Blood Volume**

Sample Type	Sample Volume (mL)	Screening (x1)	Number of Samples per Period (x 3 Periods)	End of Treatment	Total Volume (mL)
Safety Laboratory Samples (a)	12.5	1	--	1	25
Hepatitis Panel	5	1	--		5
FSH (b)	3	1	--		3
PK Samples	6	--	9	--	54
DNA Sample	6	--	1 (c)	--	6
RNA Samples	5	--	6	--	30
Total Blood Sampling Volume (per Study)					123

(a) Includes Hematology, serum chemistry, and coagulation panel.

(b) FSH level will be obtained for female subjects at Screening if they are postmenopausal (i.e. last regular menstrual cycle >2 years) and not surgically sterile.

(c) Only collected in Day 1, Period 1.

The maximum volume of blood at any single day is approximately 40 mL, and the approximate total volume of blood for the study is approximately 123 mL.

Direct venipuncture is the preferred method of blood collection. Any other method will need to be approved by the Sponsor.

## 9.0 PRETREATMENT EVENTS AND ADVERSE EVENTS

### 9.1 Definitions

#### 9.1.1 PTEs

A PTE is defined as any untoward medical occurrence in a clinical investigation subject who has signed informed consent to participate in a study but prior to administration of any study medication; it does not necessarily have to have a causal relationship with study participation.

#### 9.1.2 AEs

An AE is defined as any untoward medical occurrence in a clinical investigation subject administered a drug; it does not necessarily have to have a causal relationship with this treatment.

An AE can therefore be any unfavorable and unintended sign (e.g., a clinically significant abnormal laboratory finding), symptom, or disease temporally associated with the use of a drug whether or not it is considered related to the drug.

#### 9.1.3 Additional Points to Consider for PTEs and AEs

An untoward finding generally may:

- Indicate a new diagnosis or unexpected worsening of a pre-existing condition. (Intermittent events for pre existing conditions or underlying disease should not be considered PTEs or AEs.)
- Necessitate therapeutic intervention.
- Require an invasive diagnostic procedure.
- Require discontinuation or a change in dose of study medication or a concomitant medication.
- Be considered unfavorable by the investigator for any reason.
- PTEs/AEs caused by a study procedure (e.g., a bruise after blood draw) should be recorded as a PTE/AE.

Diagnoses vs signs and symptoms:

- Each event should be recorded to represent a single diagnosis. Accompanying signs (including abnormal laboratory values or ECG findings) or symptoms should NOT be recorded as additional AEs. If a diagnosis is unknown, sign(s) or symptom(s) should be recorded appropriately as a PTE(s) or as an AE(s).

Laboratory values and ECG findings:

- Changes in laboratory values or ECG parameters are only considered to be PTEs or AEs if they are judged to be clinically significant (i.e., if some action or intervention is required or if the investigator judges the change to be beyond the range of normal physiologic fluctuation). A laboratory re-test and/or continued monitoring of an abnormal value are not considered an

intervention. In addition, repeated or additional noninvasive testing for verification, evaluation or monitoring of an abnormality is not considered an intervention.

- If abnormal laboratory values or ECG findings are the result of pathology for which there is an overall diagnosis (e.g., increased creatinine in renal failure), the diagnosis only should be reported appropriately as a PTE or as an AE.

Pre-existing conditions:

- Pre-existing conditions (present at the time of signing of informed consent) are considered concurrent medical conditions and should NOT be recorded as PTEs or AEs. Baseline evaluations (e.g., laboratory tests, ECG, X-rays etc.) should NOT be recorded as PTEs unless related to study procedures. However, if the subject experiences a worsening or complication of such a concurrent condition, the worsening or complication should be recorded appropriately as a PTE (worsening or complication occurs before start of study medication) or an AE (worsening or complication occurs after start of study medication). Investigators should ensure that the event term recorded captures the change in the condition (e.g., “worsening of...”).
- If a subject has a pre-existing episodic condition (e.g., asthma, epilepsy) any occurrence of an episode should only be captured as a PTE/AE if the episodes become more frequent, serious or severe in nature, that is, investigators should ensure that the AE term recorded captures the change in the condition from Baseline (e.g. “worsening of...”).
- If a subject has a degenerative concurrent condition (e.g., cataracts, rheumatoid arthritis), worsening of the condition should only be captured as a PTE/AE if occurring to a greater extent to that which would be expected. Again, investigators should ensure that the AE term recorded captures the change in the condition (e.g., “worsening of...”).

Worsening of PTEs or AEs:

- If the subject experiences a worsening or complication of a PTE after starting administration of the study medication, the worsening or complication should be recorded appropriately as an AE. Investigators should ensure that the AE term recorded captures the change in the condition (e.g., “worsening of...”).
- If the subject experiences a worsening or complication of an AE after any change in study medication, the worsening or complication should be recorded as a new AE. Investigators should ensure that the AE term recorded captures the change in the condition (e.g., “worsening of...”).

Changes in severity of AEs /Serious PTEs:

- If the subject experiences changes in severity of an AE/serious PTE, the event should be captured once with the maximum severity recorded.

Preplanned surgeries or procedures:

- Preplanned procedures (surgeries or therapies) that were scheduled prior to signing of informed consent are not considered PTEs or AEs. However, if a preplanned procedure is performed early (e.g., as an emergency) due to a worsening of the pre-existing condition, the

worsening of the condition should be captured appropriately as a PTE or an AE. Complications resulting from any planned surgery should be reported as AEs.

Elective surgeries or procedures:

- Elective procedures performed where there is no change in the subject's medical condition should not be recorded as PTEs or AEs, but should be documented in the subject's source documents. Complications resulting from an elective surgery should be reported as AEs.

Overdose:

- Cases of overdose with any medication without manifested side effects are NOT considered PTEs or AEs, but instead will be documented on an Overdose page of the eCRF. Any manifested side effects will be considered PTEs or AEs and will be recorded on the AE page of the eCRF.
- Suicidal Ideation and Behavior:
- A completed suicide is always a SAE based on its fatal outcome. C-SSRS score of 4 (active suicidal ideation with some intent to act) or 5 (active suicidal ideation with specific plan and intent) would likely indicate serious suicidal ideation and can be used to trigger intervention procedures to provide urgent care. Such procedures may include further evaluation and appropriate management; and/or immediate contact with (or need for a referral to) the subject's mental health practitioner; and/or possible referral to the emergency room; and/or admission to an in-subject unit. For the purpose of this protocol active suicidal ideation level 4 and 5 should be considered important medical events and reported as serious irrespective of whether the subject was hospitalized or not.
- Unless the event meets other serious criteria, suicidal thoughts or suicidal ideations that do not include a definite plan or intention to act will be collected as non-serious adverse events in accordance with the standard AE reporting requirements (e.g., if a pre-existing suicidal ideation recorded on the screening C-SSRS got worse during the study, it should be reported as an AE).
- A subject presenting with self-mutilation or other types of self-injury should be questioned by the investigator to clarify if the action was suicidal in intent. If the event was suicidal in intent, the investigator should include suicidal behavior as part of the verbatim term on the eCRF, that is, "slit wrists/suicidal behavior". Such an event will be collected as a serious adverse event.
- Acts of self-mutilation or self-injury without suicidal intention (i.e., self-imposed cigarette burns), will be collected as non-serious adverse events, unless they meet other seriousness criteria.

#### 9.1.4 SAEs

An SAE is defined as any untoward medical occurrence that at any dose:

1. Results in DEATH.
2. Is LIFE THREATENING.

- The term “life threatening” refers to an event in which the subject was at risk of death at the time of the event; it does not refer to an event that hypothetically might have caused death if it were more severe.

3. Requires inpatient HOSPITALIZATION or prolongation of existing hospitalization.
4. Results in persistent or significant DISABILITY/INCAPACITY.
5. Is a CONGENITAL ANOMALY/BIRTH DEFECT.
  - Report if you suspect that exposure to a medical product prior to conception or during pregnancy may have resulted in an adverse outcome in the child.
6. Is an IMPORTANT MEDICAL EVENT that satisfies any of the following:
  - May require intervention to prevent items 1 through 5 above.
  - May expose the subject to danger, even though the event is not immediately life threatening or fatal or does not result in hospitalization.
  - Includes any event or synonym described in the Medically Significant AE List ([Table 10.a](#)).

**Table 10.a Medically Significant AE List**

Term	
Acute respiratory failure/acute respiratory distress syndrome	Hepatic necrosis
Torsade de pointes / ventricular fibrillation / ventricular tachycardia	Acute liver failure Anaphylactic shock
Malignant hypertension	Acute renal failure
Convulsive seizure	Pulmonary hypertension
Agranulocytosis	Pulmonary fibrosis
Aplastic anemia	Confirmed or suspected endotoxin shock
Toxic epidermal necrolysis/Stevens-Johnson syndrome	Confirmed or suspected transmission of infectious agent by a medicinal product Serotonin syndrome Neuroleptic malignant syndrome / malignant hyperthermia Spontaneous abortion / stillbirth and fetal death

PTEs that fulfill 1 or more of the serious criteria above are also to be considered SAEs and should be reported and followed up in the same manner (see [Sections 10.2.2](#) and [10.3](#)).

### 9.1.5 Severity of PTEs and AEs

The different categories of intensity (severity) are characterized as follows:

Mild: The event is transient and easily tolerated by the subject.

Moderate: The event causes the subject discomfort and interrupts the subject's usual activities.

Severe: The event causes considerable interference with the subject's usual activities.

### **9.1.6 Causality of AEs**

The relationship of each AE to study medication(s) will be assessed using the following categories:

Related: An AE that follows a reasonable temporal sequence from administration of a drug (including the course after withdrawal of the drug), or for which possible involvement of the drug cannot be ruled out, although factors other than the drug, such as underlying diseases, complications, concomitant drugs and concurrent treatments, may also be responsible.

Not Related: An AE that does not follow a reasonable temporal sequence from administration of a drug and/or that can reasonably be explained by other factors, such as underlying diseases, complications, concomitant drugs and concurrent treatments.

### **9.1.7 Relationship to Study Procedures**

Relationship (causality) to study procedures should be determined for all PTEs and AEs.

The relationship should be assessed as Related if the investigator considers that there is reasonable possibility that an event is due to a study procedure. Otherwise, the relationship should be assessed as Not Related.

### **9.1.8 Start Date**

The start date of the AE/PTE is the date that the first signs/symptoms were noted by the subject and/or physician.

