## **8.2 Monitoring Subject Treatment Compliance**

Study medication will be administered while subjects are under observation in the clinical research unit. Following administration of the study medication, appropriate mouth and/or hand checks will be performed to ensure that the dose is swallowed and noted in the source document. The date and time of each dose will be recorded in the source documents and on the eCRFs. An inventory of the study medication supplies dispensed will be performed by the site pharmacist or authorized study designee and recorded onto the Drug Accountability Log in the subject's source document records or equivalent. The exact dose time of consecutive subjects may be staggered to facilitate logistics at the site.

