## 9.2 Procedures

### 9.2.1 Collection and Reporting of AEs

#### 9.2.1.1 PTE and AE Collection Period

Collection of PTEs will commence from the time the subject signs the informed consent to participate in the study and continue until the subject is first administered study medication on Day 1 Period 1 of Part 2 or until screen failure. For subjects who discontinue prior to study medication administration, PTEs are collected until the subject discontinues study participation.

Collection of AEs will commence from the time that the subject is first administered study medication Day 1 Treatment Period 1. Routine collection of AEs will continue until 21 days following last dose.

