#### 9.2.1.2 PTE and AE Reporting

At each study visit, the investigator will assess whether any subjective AEs have occurred. A neutral question, such as “How have you been feeling since your last visit?” may be asked. Subjects may report AEs occurring at any other time during the study. Subjects experiencing a serious PTE must be monitored until the symptoms subside and any clinically relevant changes in laboratory values have returned to Baseline or there is a satisfactory explanation for the change. Non-serious PTEs, related or unrelated to the study procedure, need not to be followed-up for the purposes of the protocol.

All subjects experiencing AEs, whether considered associated with the use of the study medication or not, must be monitored until the symptoms subside and any clinically relevant changes in laboratory values have returned to Baseline or until there is a satisfactory explanation for the changes observed. All PTEs and AEs will be documented in the PTE/AE page of the

eCRF, whether or not the investigator concludes that the event is related to the drug treatment. The following information will be documented for each event:

1. Event term.
2. Start and stop date.
3. Frequency.
4. Severity.
5. Investigator's opinion of the causal relationship between the event and administration of study medication(s) (related or not related) (not completed for PTEs).
6. Investigator's opinion of the causal relationship to study procedure(s), including the details of the suspected procedure.
7. Action concerning study medication (not applicable for PTEs).
8. Outcome of event.
9. Seriousness.

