#### **12.1.5 Safety Analysis**

The Safety Set will be used for all summaries of TEAEs, laboratory tests, and vital signs. All safety data will be summarized by treatment.

AEs will be presented in listings. TEAEs will be classified according to system organ class and preferred term and will be tabulated with a breakdown by treatment and by event severity. Similar TEAE tabulations will be performed on those events assessed by the investigator as related to study drug.

Individual results of vital signs will be listed and observed values and changes from Baseline in vital signs will be summarized by treatment.

Physical exam findings, suicidality assessments (C-SSRS), and PANSS scores will be presented in data listings.

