## Appendix A Schedule of Study Procedures

Study Day:	Visit 1: Screening	CVN058 and Placebo Treatment Periods 1, 2, and 3 (a)		End of Treatment Period 3, End Day 1	Early Termination (c)	Follow-up Day 7-10 After End of Treatment (b)
		Day 1 pre-dose	Day 1 post-dose			
Informed consent	X					
Inclusion/exclusion criteria	X	X				
Demographics and medical history	X					
Medication history	X					
Physical examination	X	X		X	X	
Vital signs (d)	X	X	X		X	
Weight, height, and BMI (e)	X			X	X	
Concomitant medications (f)	X	X	X		X	X
Concurrent medical conditions (g)	X					
Clinical laboratory tests (h)	X			X	X	
Hepatitis panel	X					
Audiometric Screening and Tone Matching test (i)	X					
FSH (j)	X					
Pregnancy test (hCG), serum except as noted	X	X (urine)			X	
Urine drug and saliva alcohol screen	X					
ECG	X					
EEG battery (k)			X			
MMN (l)			X			
DNA sample collection (m)		X				
RNA sample collection (n)		X	X			
PK blood collection (o)		X	X		X	
Study drug dosing (p)			X			
PTE assessment (q)	X	X				
AE assessment (r)			X		X	X
C-SSRS (s)	X		X		X	
PANSS (t)	X		X		X	

Footnotes are on last table page.

- (a) Minimum 7-day and maximum 10-day washout period is required in between Treatment Periods 1, 2 and 3.
- (b) The Follow-up Visit will occur by telephone 7-10 days after End of Treatment unless abnormal, clinically significant findings were observed upon discharge. In these cases, subjects must then be brought back to the clinic for re-evaluation per investigator's discretion.
- (c) Conduct procedures for subjects discontinued early per Protocol [Section 7.6](#). The PK sample should be collected at the Early Termination Visit, if within 1 hour of a scheduled PK time point.
- (d) Vital signs (oral temperature, respiration, pulse, and blood pressure) will be obtained at Screening, and in Periods 1, 2, and 3 (pre dose [within 30 minutes prior to dosing], and at 1 and 5 hours post dose), and at Early Termination (if applicable), and if clinically indicated according to Investigator discretion at the Follow-up visit.
- (e) Height and BMI will be collected at Screening only.
- (f) Record all patient medications from Screening and throughout the study.
- (g) All new concurrent medical conditions arising post-oi should be recorded as PTE or AE.

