- (h) Clinical laboratory tests (hematology, serum chemistry, and urinalysis) will be collected at Screening and prior to check-out at End of Treatment or Early Termination, and at the Investigator discretion if a Follow-up Visit is indicated.
- (i) Audiometric Screening assessment conducted according to local practice.
- (j) A FSH level will be obtained on post menopausal women (defined as continuous amenorrhea of at least 2 years and not surgically sterile).
- (k) For the EEG battery, testing will be done at Day 1 starting approximately 1.5 hours post dose for each period and will last approximately 3 hours. NOTE: Subjects should refrain from drinking coffee and smoking approximately 1 hour prior to the EEG assessment until discharge from clinic at the end of the afternoon.
- (l) MMN will be the first EEG assessment conducted in the battery.
- (m) One blood sample (6 mL) will be collected for pharmacogenomic analysis prior to study drug administration on Day 1 of Period 1 only. If isolation of DNA from the first sample was not successful or possible, a second aliquot of blood may be taken, if feasible.
- (n) Two 2.5 mL whole blood samples will be collected for each Period (Periods 1, 2, and 3) on Day 1 at pre-dose, and 5 hours post-dose.
- (o) Blood samples (6 mL) for PK analyses will be collected at pre -dose (within 15 minutes prior to dosing), and 1 and 5 hours post dose.
- (p) Dosing will only occur on Day 1 of each period, and signals the start of the post-dose Day 1 visit assessments.
- (q) PTEs will be collected from signing of informed consent up until dosing on Day 1.
- (r) Any adverse event with onset or exacerbation after dosing on Day 1 of Period 1 will be captured as an AE or SAE.
- (s) The Screening/Baseline C-SSRS will be administered at Screening and the Since Last Visit C-SSRS will be administered after EEG/ERP collection on each dosing day, and End of Treatment or Early Termination (if applicable).
- (t) The Screening/Baseline PANSS will be collected at Screening, approximately 5 hours after each dose (post EEG) and at Early Termination (if applicable).

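### AE onset is recorded by date only, and Appendix A marks PTE but not AE assessment before the Period 2 and 3 doses, so an event first noted on those two dates cannot be placed before or after the dose

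*Protocol*

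**What the plan says.** Section numbers are those of Version 2.0. Version 1.0 has the same content on this point in 9.2, 10.1.8, 10.2.1.1, 10.2.1.2, 13.1.5 and Appendix A.

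- **Onset.** Section 9.1.8 states: "The start date of the AE/PTE is the date that the first signs/symptoms were noted by the subject and/or physician". Section 9.2.1.2 lists nine items to document for each event. The only timing item is "Start and stop date".
- **Dose.** Section 8.2 is more precise: "The date and time of each dose will be recorded in the source documents and on the eCRFs".
- **Start of AE collection.** Section 9.2.1.1 states: "Collection of AEs will commence from the time that the subject is first administered study medication Day 1 Treatment Period 1". It ends PTE collection at that same first dose. Appendix A footnote (r) agrees: anything starting or worsening after the Period 1 dose is an AE or SAE. Section 9.2.1.2 adds that the investigator asks about AEs at every study visit.
- **Schedule.** The Day 1 pre-dose column of Appendix A sits under a heading that covers Treatment Periods 1, 2 and 3. It has a mark for PTE assessment and none for AE assessment. AE assessment is marked post-dose, at Early Termination and at Follow-up. Footnote (q) reads: "PTEs will be collected from signing of informed consent up until dosing on Day 1". It names no period.
- **Use of the data.** Section 12.1.5 states: "TEAEs will be classified according to system organ class and preferred term and will be tabulated with a breakdown by treatment".

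**The concern.** In this crossover each treatment is one dose on one day. The by-treatment TEAE tables therefore depend on whether an event began before or after a particular dose. The protocol gives the dose a clock time and the event only a date. When both fall on the same date, they cannot be put in order.

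The schedule adds a second problem. A site that follows the grid would treat a finding made before the Period 2 or 3 dose as a PTE, although by the text it is an AE that arose after an earlier treatment. Under Section 9.2.1.2 a PTE gets no drug-causality opinion and no action-taken entry, and a non-serious PTE need not be followed up. An event after active drug could be filed as pretreatment and drop out of the TEAE tables.

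Such findings are foreseeable. Appendix A schedules a physical examination and blood draws before dosing in each period. Section 8.1.3 has clinically significant examination changes recorded as events, and Section 9.1.3 gives a bruise from a blood draw as a recordable event.

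**Working it through.** The plan states no figure on this point, so there is none to reproduce. The check compares passages and then counts dates.

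**Step 1. Which onsets can be placed from the listed items?**

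| Onset | What separates before from after dosing | Settled? |
|---|---|---|
| Period 1 dosing date | PTE before the first dose, AE after it | Yes |
| A date between dosing dates | Onset date against dose dates | Yes |
| Period 2 or 3 dosing date | Nothing: an AE either way, with the same date | No |

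Only the last row is open. A symptom that the subject had already noticed during the washout carries its earlier date and falls in the second row. A sign first noted by the physician at the pre-dose examination takes the dosing date and falls in the third.

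**Step 2. Grid against text for the pre-dose hours of Periods 2 and 3**

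- Sections 9.2.1.1 and 9.2.1.2 and footnote (r): PTE collection has ended, any new event is an AE, and AEs are asked about at the visit.
- Appendix A grid: PTE assessment is marked and AE assessment is blank.
- Footnote (q): stops at Day 1. Every period has a Day 1 (footnote (p)), so this does not settle the matter. Footnote (m), on DNA sampling, does restrict itself explicitly to Period 1.

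The grid and the text conflict for two of the three periods.

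**Step 3. How many dates are affected?**

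Inputs: 3 dosing dates per subject; 20 completers (Section 12.2); dose interval g of 7 to 10 days (Appendix A footnote (a)); AE collection for f = 21 days after the last dose (Section 9.2.1.1), or f = 7 to 10 days if collection in practice stops at the follow-up call.

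- Open dosing dates: 2 per subject, so 20 × 2 = 40 of 20 × 3 = 60.
- Dates in AE collection per subject: 2g + f + 1. Share that is open: 2/(2g + f + 1).
- f = 21: g = 7 gives 2/36 = 5.6%; g = 10 gives 2/42 = 4.8%.
- Collection ending at the call: g = 7, f = 7 gives 2/22 = 9.1%; g = 10, f = 10 gives 2/31 = 6.5%.

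If same-day events were all counted to that day's treatment, only onsets in the hours before the dose would be misplaced, which is less than these shares suggest.

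**Step 4. Effect of one misplaced subject**

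With 20 subjects per treatment, 1/20 = 5 percentage points on that treatment's TEAE percentage. This holds only if the subject has no other TEAE on that treatment. The documents give no event rate, so an expected number of misplaced subjects cannot be calculated.

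**The case against.** The case for leaving the text alone has real substance.

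- **A convention can still assign the events.** The TEAE definition and a same-day rule are commonly set in the SAP, which is not shown, so their absence here is no fault. This stands. However, a convention cannot recover an onset time that was never collected, and it cannot correct a site's assessment schedule.
- **The eCRF may capture a time.** The protocol does not forbid it, and the eCRF is not shown. This stands: the point is about what the protocol requires.
- **The body text resolves the grid.** The pre-dose column is not uniform across periods, since DNA sampling is marked there but applies to Period 1 only. In that case, though, the footnote states the restriction. For PTEs it does not, and sites work from the schedule.
- **Early drug effects follow the dose.** Median tmax is 1 to 1.25 hours (Section 3.3) and dosing is in the morning (Section 5.1), so most dosing-day events will be post-dose. This stands and keeps the problem small.

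A reader might also infer more than the documents support:

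- *That no dosing-day event can be assigned to a treatment.* In Period 1 the PTE/AE split already does this.
- *That washout events become TEAEs of the next treatment by default.* No passage says so, and an event noted on an earlier date is assignable by that date.
- *That AEs are never asked about before dosing.* That is true of the grid only; Section 9.2.1.2 requires the question at each visit, without saying when in the visit.
- *That the secondary endpoint is compromised.* Whether a subject has at least one TEAE at all turns mainly on onset after the first dose, which the Period 1 split settles. What could be lost is an event misfiled as a PTE in Period 2 or 3.
- *That timing for causality is lost.* Dosing is observed and timed, and the investigator judges temporal sequence directly.

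**Conclusion.** The point holds within narrow limits. In Versions 1.0 and 2.0, an event first noted on the Period 2 or Period 3 dosing date cannot be shown from the listed items to precede or follow that day's dose. The Appendix A PTE and AE rows and footnote (q) also contradict the collection rules in Sections 9.2.1.1 and 9.2.1.2 and footnote (r) for those two periods. The exposure is two dates per subject, about 5% to 9% of AE-collection dates depending on when collection ends. The consequence is confined largely to the by-treatment TEAE tables. It is worth correcting because the tables are small and the grid could send an AE to the wrong category, not because the safety assessment as a whole fails.

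This rests on two assumptions: that the eCRF collects no more than the protocol lists, and that sites follow the grid. Later versions could not be checked. The documents list versions up to 5.0, but the third copy breaks off before its adverse event section and its Appendix A.

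**What to change.** 1. In the list of items recorded for each event, add onset time, or a before/after-dose flag, for events starting on a dosing day. Dose time is already recorded.
2. In Appendix A, limit pre-dose PTE assessment to Period 1, and say so in footnote (q).
3. In Appendix A, mark AE assessment in the pre-dose column for Periods 2 and 3.
4. In the by-treatment tables, assign each event to the last dose given before its onset.

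The cost is one eCRF field, edits to two rows of the grid and one footnote, and one sentence on attribution. The downside is slightly more data entry on dosing days. If a later version already has these changes, nothing further is needed.
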